5.3 Study Duration

Total duration of the study for each patient will be 7 days (+7 days) including follow-up 24-72 hrs. after the final study related procedure.

Total anticipated study duration, including data analysis and final report, is estimated to be up to 12 months.

5.4 Inclusion Criteria

The inclusion criteria for this study are:

1. Patient is 18-75 years
2. Patient is able to provide informed consent
3. Patient has appropriate indications for EGD including symptoms of, but not limited to upper abdominal pain, acid reflux, heartburn, iron deficiency anemia, weight loss, bloating, belching, nausea, vomiting and atypical chest pain.
4. Patients are COVID-19 negative by PCR testing 1-3 days prior to MCC/MCC-T and EGD or fully vaccinated against SARS-CoV-2 (at least two weeks after final dose of authorized or approved vaccine) and completion of a symptom screening questionnaire before participating in the study.

5.5 Exclusion Criteria

The exclusion criteria for this study are:

1. Patient with dysphagia.

2. Patient with previous intestinal surgery.
3. Patient with Crohn's disease or other potential obstructive conditions, unless there is a recent CTE, MRE or patency capsule performed to exclude an obstructive lesion that may retain the capsule.
4. Female patient is pregnant.
5. Patient with implanted medical device that would be potentially affected by magnets or radiofrequency emissions (e.g., pacemakers, implanted cardiac defibrillators).
6. COVID-19+ or with symptoms consistent with the infection. Fever, new cough, myalgias, and chills

5.6 Informed Consent

All potential subjects will receive a comprehensive explanation regarding the study and associated procedures. Patients meeting the eligibility criteria will receive a copy of the informed consent form and given sufficient time to determine whether they would like to participate in the study. All patients enrolled in the study must sign and date the informed consent form and receive a copy of the signed form for their records.

5.7 Patient Identification and Confidentiality

[figure not shown]
Patients will be identified on all CRFs by a unique study number. CRFs are confidential documents and will only be available to the sponsor, the Investigator, Investigators' staff, the Investigation statistician, and, if requested, to regulatory authorities. The Investigator will maintain as part of the investigation file a list identifying all patients entered into the trial.

5.8 Screening Failure

Patients who have not fulfilled all the inclusion criteria or have fulfilled one of the exclusion criteria will not be included in this study. Screening failures will be replaced by suitable candidates.

6 STUDY PROCEDURES

6.1 Diagram of Study Flow

6.2 Table of Procedure Schedule

Assessment	Pre-screening	Visit 1 Screening Enrollment	Patient data extraction	Visit 2 MCC-T Procedure	Visit 3 EGD	Visit 4 Telephone Follow-up & Termination
Recruitment and Informed Consent review	X	X				
Sign informed consent		X				
PCR for COVID-19 if not fully vaccinated				X*	X*	
Symptom screening for COVID-19		X		X	X	
Inclusion/Exclusion Criteria	X	X				
Demographic & Medical History		X	X			
Physical Examination		X				
Concomitant Medication		X				
Enrollment		X				
MCC procedure		X		X		
EGD procedure					X	
Patient satisfaction/preference questionnaire						X
Adverse events evaluation				X	X	X
Identification of relevant lesions	On a weekly basis					
Exit Form						X

*COVID testing must be completed 24-72 hours prior to the procedure if required. If, due to scheduling, the NaviCam and EGD cannot be scheduled on the same day or the next day, the COVID test may need to be repeated.

All collected parameters and comments will be documented in the CRF.

6.3 Recruitment

Approximately 400 patients a month are seen in the UMass Gastroenterology clinic or are referred for EGD with complaints of upper abdominal pain requiring an upper endoscopy. These patients will be screened for possible inclusion in the study the day prior to their visit to the clinic. This number is subject to change due to the COVID-19 epidemic.

6.4 Visit 1 – Screening and Enrolment

Patients found to be potential study candidate will be flagged and contacted by a study nurse before their visit. The study coordinator will review the study with the patient. If patients show interest in being involved in the study, a visit will be arranged at which consent will be obtained and a PCR and symptom survey will be performed. If negative, a time and date for the MCC and EGD procedures will be arranged.

The MCC or MCC-T will be performed first followed by an EGD at least 2-3 hours later, but up to 7 days later.

A member of study staff will then extract all relevant demographic data from the patients' medical record to the patient CRF. Relevant demographic data includes but is not limited to date of birth, height, weight, gender, race, past medical history, past surgical history, medications and allergies.

6.5 Visit 2 – MCC, MCC-T and EGD Procedure

Upon being checked in, the subject will be brought to the study area with the NaviCam System. A study staff member (NP/Attending/Fellow) trained in the MCC-T procedure will review the study procedure with the patient and confirm that the patient has been NPO for at least 8 hours. The patient will drink about 250ml of water prior to ingesting the capsule containing 1-2 drops of simethicone (infant formulation).

Examination of Esophagus:

The sensor array jacket will be attached to the patient. After the capsule is activated the patient will swallow the capsule (attached to a tether) in the sitting position. It will then be slowly lowered down the esophagus for a complete exam. Alternatively, the patient will be placed in the prone position with a 10° elevation of the head and ingest the capsule without the tether using sips of water. The study staff member will then record the video of the examination of the esophagus by moving the capsule down the esophagus using the magnetic field.

Images to be obtained:

1. Upper esophagus

2. Middle esophagus
3. Lower esophagus
4. Z line.
5. Any pathological lesions

Examination of Stomach:

Once the examination of the esophagus is complete and the capsule is in the stomach, the tether, if used, will be used to view the stomach as the patient drinks about 500 to 1000 cc of water with 4 drop of simethicone to ensure adequate gastric distention. The tether is then detached from the capsule by injecting air through the tether causing separation of the two components. The tether is withdrawn. Then instructed to lay down per physician instructions. The study staff member will begin controlling the device using the magnetic system. The patient will move their position in a predetermined patent to enhance complete visualization of the stomach as was done in the esophagus, a video will be recorded of the full examination. Photo documentation in accordance with a gastric mapping protocol will also be done. This includes images of the following:

- Distal Antrum
- Centered view of the pylorus
- Proximal Antrum
- Two pictures along the length of the incisura
- Distal body
- Mid/proximal body (lesser curvature)
- Mid/Proximal body (greater curvature)
- Gastric fundus
- Gastric cardia
- Any gastric pathology (e.g. gastric varices, gastric ulcers, gastropathy, polyps, etc.)

Examination of duodenum:

Once the final images have been obtained the capsule will be piloted through the pylorus and into the duodenum. Following a brief examination (with photo documentation) of the duodenal bulb the capsule will be released into the small intestine with the video still running. Once the capsule reaches the distal duodenum the video recording can then stop, and the examination is completed.

Recording of MCC procedure:

The responsible study staff member will generate a procedure report documenting his/her findings that will then be cosigned by the study staff attending. This document will be deidentified and only linked to the patient by their study ID number. The document will be placed in the patient's study file along with the video recording of the entire procedure. The patient must be blinded to the findings at this time.

EGD Procedure:

At least two hours after the MCC-T ingestion the subject will be brought to the endoscopy procedure area; study staff will confirm that the patient has been NPO for at least 2 hours after the ingestion of water for the MCC or MCC-T procedure. If practicable, both procedures may be performed on the same day. If not, the EGD will be performed within 7 days and the patient will need to fast overnight prior to the EGD appointment and have nothing by mouth for at least 2 hours prior to arrival (per standard EGD instructions).

The patient will then be sedated using conscious sedation with midazolam and fentanyl or monitored anesthesia with propofol. The upper endoscopy will be performed in the left lateral position. The same photos of the esophagus, stomach, and duodenum will be obtained as described above. The doctor performing the upper endoscopy will not have any knowledge of the findings of the MCC procedure. The patient is then allowed to recover for 30 minutes in the recovery room and discharged.

Image management

Images from the MCC-T procedure will be stored in the Navicam system.

Images of the endoscopic procedure will be stored in Provation and EPIC as per routine.

Images from the MCC, MCC-T and EGD will be printed on photographic paper for comparison by the study team.

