6.7 Identification of relevant lesions

On a weekly basis, 2 study attendings will independently review the results of the EGDs/MCCs that were performed during the week and complete a report sheet. A per-patient analysis of any abnormal lesion/s will be performed. During this analysis, the physicians will be asked if either the MCC or MCC-T or the EGD identified a lesion that would be of high likelihood to explain the patient's symptoms. If a responsible lesion is identified, then the physicians will review both the MCC and EGD to see if the lesion(s) were identified on both exams. Findings will be graded on a three-tier scale as follows:

- **D0:** finding is unlikely to be related to patient's presenting complaint
- **D1:** finding is of a medium likelihood to be related to the patient's presenting complaint
- **D2:** finding is of a high likelihood to be related to the patient's presenting complaint.

In addition, reviewing group will be responsible to perform a per-lesion analysis to assess whether all findings identified on the MCC and/or EGD were seen on the other exam (regardless of whether the finding is relevant to the patient's complaint). The statistician will then compare the results and obtain a Kappa statistic of the three sets of observations. And perform a statistical analysis as outlined under the analysis section.

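### The capsule report has no deadline before EGD, its author and cosigner are not kept from the EGD result, and section 6.7 does not tie capsule positivity to an EGD-blind report

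*Combined protocol and SAP*

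**What the plan says.** Section 6.4 fixes the order of the two tests: "The MCC or MCC-T will be performed first followed by an EGD at least 2-3 hours later, but up to 7 days later". Section 6.5 adds "If practicable, both procedures may be performed on the same day".

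Under the recording heading of 6.5, the person responsible for the capsule examination "will generate a procedure report documenting his/her findings that will then be cosigned by the study staff attending". The report is filed with the video. Two statements there concern access to it: "The patient must be blinded to the findings at this time", and "This document will be deidentified and only linked to the patient by their study ID number". Under the EGD heading comes the only rule on blinding between the tests: "The doctor performing the upper endoscopy will not have any knowledge of the findings of the MCC procedure". EGD images are kept in the hospital's routine systems, and no access limit is stated for capsule staff. The title calls the study single blinded without saying who is blinded.

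In section 6.7 two attendings review the week's capsule and EGD results, and "the physicians will be asked if either the MCC or MCC-T or the EGD identified a lesion" likely to explain the symptoms. They then go back to both exams to see whether each showed it. A per-lesion comparison follows, in which findings on either exam are looked for on the other.

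The primary endpoint (synopsis, 4.2 and 10.5) is built on D2 findings: sensitivity, specificity, predictive values and McNemar's test, with the expert group's decision as the reference. Section 10.1 names EGD as the reference instead.

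**The concern.** In a tandem accuracy study each test's result should be fixed before anyone who shapes it knows the other result. Here that is stated for EGD and not for the capsule. Reporting has two steps, writing and cosigning, and neither has a time limit. Nothing stops the cosigning attending from being the person who performed that patient's EGD. Removing the patient's identity from the report does not hide the EGD result from someone who was there or who can open the record.

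If the capsule result is completed in the light of EGD, a lesion seen only by EGD can become one seen by both. Such discordant pairs are what McNemar's test uses, and in a study of this size there are few of them. A capsule finding that EGD did not confirm can also be dropped. Either change alters the primary comparison, and no time stamp is required that would show when a finding was first recorded.

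**Working it through.** The plan gives no lesion rate, sensitivity, alpha or power, so it has no figure to reproduce. The check has a textual part and an illustration.

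**Text: who is kept from what**

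| Person | Kept from the other test's result? | Where |
|---|---|---|
| Endoscopist | Yes, from the capsule findings | 6.5, EGD procedure |
| Patient | Yes, from the capsule findings, for the time being | 6.5, recording |
| Capsule report author | Not stated | – |
| Cosigning attending | Not stated | – |
| Weekly review attendings | No, both exams are in view | 6.7 |

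No section gives a time by which the capsule report must be written, cosigned or locked.

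**Illustration: inputs**
- 70 patients: section 10.6. Other sections give other totals, but the number cancels out of the sensitivities.
- Assumed, not in the documents: 30% D2-positive, EGD sensitivity 90%, capsule sensitivity 80%, independent misses, no false positives in other patients.
- Reference (expert-group reading): a lesion counts if either test reports it.

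**Expected counts**
- D2-positive: 70 × 0.30 = 21
- Seen by both: 21 × 0.9 × 0.8 = 15.12
- EGD only: 21 × 0.9 × 0.2 = 3.78
- Capsule only: 21 × 0.1 × 0.8 = 1.68
- Reference-positive: 15.12 + 3.78 + 1.68 = 20.58
- Capsule sensitivity: (15.12 + 1.68) / 20.58 = 81.6%
- EGD sensitivity: (15.12 + 3.78) / 20.58 = 91.8%

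**Effect of late edits**, with dropped lesions leaving the reference:

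| Late edits | EGD only | Capsule only | Reference-positive | Capsule | EGD | Gap (points) |
|---|---|---|---|---|---|---|
| None | 3.78 | 1.68 | 20.58 | 81.6% | 91.8% | 10.2 |
| Quarter of EGD-only added (0.945) | 2.835 | 1.68 | 20.58 | 86.2% | 91.8% | 5.6 |
| Half of EGD-only added (1.89) | 1.89 | 1.68 | 20.58 | 90.8% | 91.8% | 1.0 |
| Half of capsule-only dropped (0.84) | 3.78 | 0.84 | 19.74 | 80.9% | 95.7% | 14.9 |
| Half added and half dropped | 1.89 | 0.84 | 19.74 | 90.4% | 95.7% | 5.3 |

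For example, the last row is (16.80 + 1.89 − 0.84) / 19.74 = 17.85 / 19.74 = 90.4%.

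**Same edits with EGD as the reference (10.1).** EGD-positive: 18.9. EGD-negative: 70 − 18.9 = 51.1.
- Capsule sensitivity is 15.12 / 18.9 = 80.0%. With half of the EGD-only lesions added it is 17.01 / 18.9 = 90.0%.
- Capsule specificity is (51.1 − 1.68) / 51.1 = 96.7%. With half of the capsule-only lesions dropped it is (51.1 − 0.84) / 51.1 = 98.4%.

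Additions therefore help the capsule under both references. Deletions help it when EGD is the reference and can hurt it under the expert-group reference.

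**McNemar's test**, under a second set of assumptions (70 patients, 30% D2-positive, EGD 95% and capsule 70% sensitive, exact two-sided test, alpha 0.05). Expected EGD-only patients are 21 × 0.95 × 0.30 = 5.99, and capsule-only patients 21 × 0.05 × 0.70 = 0.74. Adding a quarter or half of the EGD-only lesions cuts the former to 4.49 or 2.99, and power from 0.37 to 0.17 or 0.04. Over 20% to 40% prevalence, power without edits is 0.14 to 0.57; with half added it is 0.01 to 0.10.

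**The case against.** The strongest reply is that sequence already protects the capsule. It always comes first, it is steered live, and lesions are photographed during the examination, so image capture and live impressions cannot be influenced by EGD. Section 6.5 describes the report, the cosignature and the filing before it turns to EGD, and the rule for the endoscopist presupposes that capsule findings exist by then. This stands as evidence of intent. It is not a requirement, and it does not cover re-reading of the video or a later cosignature. The flow diagram in 6.1 and the appended timeline cannot be seen here, so whether they show report timing is unknown.

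Four stronger readings are tempting and are not supported:

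- *That the operator's report is what feeds the primary endpoint.* No section says so. Section 6.7 speaks of results and of reviewing both exams, and 6.5 and section 10 describe comparison of printed or de-identified images. If the attendings score images, late report wording may not matter, but their own reading is then made with EGD in view.
- *That the bias must favour the sponsor's device.* This follows for additions. For deletions it depends on the reference standard, which the plan states in two ways.
- *That a late change could never be detected.* The full video and the stored capsule images are kept, so an added lesion can be checked for visibility. They cannot show when it was first recognised.
- *That EGD will often start while the capsule is still recording.* Section 6.5 asks for two hours after ingestion and also two hours after the procedure water. No transit time is given, so routine overlap is not shown.

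It is also fair to say that a lock alone would change nothing while 6.7 lets the attendings decide, with both exams in view, what the capsule showed.

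**Conclusion.** The concern holds as a gap in the rules, not as a planned late report. Followed to the letter, the plan permits a capsule result informed by EGD at two points: when the report is written or cosigned, and when the 6.7 attendings check the capsule exam for EGD's lesions.

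The documents do not allow the bias to be sized or its net direction fixed. Under the assumptions shown, about two added lesions (1.89 expected) shrink a 10.2-point sensitivity gap to 1.0. If half of the capsule-only lesions are also dropped, the gap is 5.3 points. These figures rest on assumed prevalence, sensitivities, independence and edit shares, and show only that one or two edits matter in a study of 70 patients. The change is worth making because it is cheap and protects the primary comparison.

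**What to change.** - **Section 6.5:** require the capsule report to be completed, cosigned and locked with a time stamp in REDCap before EGD begins. Author and cosigner remain unaware of that patient's EGD result until the lock.
- **Section 6.7:** take capsule detection in the primary analysis from the locked report. The attendings grade relevance (D0 to D2) and do not decide afresh whether the capsule showed the lesion. Later capsule findings are dated addenda, reported separately and not counted as capsule detections.
- **Analysis:** flag any report locked after the start of EGD as a protocol deviation, and repeat the primary analysis without those patients.

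The cost is protocol wording and one time-stamped lock in the data system already in use. A same-day EGD may sometimes have to wait for the cosignature. The cosigner must be an attending who has not seen that patient's EGD; the documents do not say how many attendings are available, so whether this needs extra cover is unknown. Capsule sensitivity may look slightly less favourable than it would with re-reading allowed.

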6.6 Visit 4 – Telephone Follow-up and Termination

24 hours after all procedures are completed the study coordinator will call the patient and briefly go through a standardized form of questions. Most importantly, the study coordinator will ask the patient which procedure they preferred and would be more agreeable to having done again (Questionnaire provided in Appendix I).

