With respect to performance, the MCC was found to be equivalent to conventional gastroscopy in visualizing gastric mucosa. A total of 9 adverse events were reported in 5 (1.4%) of the 350 patients who completed this study. Three patients had abdominal distension and nausea, 1 patient had headache and vomiting, and 1 patient had foreign body sensations. In 4 of these 5 patients, adverse events including abdominal distension, nausea, vomiting, and headache were considered to be related to gastric preparation. All reported symptoms were resolved within 24 hours after ingestion of the capsule. Moreover, because of the noninvasiveness of the MCC procedure, more than 95% of patients preferred the MCC procedure as an initial diagnostic method.

Out of a total of 449 patients, only 5 patients reported mild adverse events which were all resolved within 24 hours. These results indicate that the MCC is safe, and any risks associated with the device and procedure are negligible when compared to the benefits of a minimally invasive procedure.

Additionally, a study utilizing the tether device was conducted in Changhai Hospital on 4 healthy volunteers and 21 patients with suspected esophageal disease. The MCC-T using the tether device was successfully carried out in all 25 participants. No adverse events were observed. Mean overall discomfort score during the procedure was 0.96 (range 0 – 3). NaviCam System diagnoses were in accordance with EGD in all 25 participants. The per-patient sensitivity of the NaviCam for esophageal disease detection was 100 %. The accuracy of the NaviCam for grading esophageal varices and reflux esophagitis were 66.7% and 100 %, respectively. (Unpublished). Additional unpublished data in volunteers has demonstrated that by moving the magnet over the chest with the patient in the prone position the MCC can be slowed down while it transits the esophagus.

On May 22, 2020 the company obtained FDA approval for the MCC device.

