4.2 Study Endpoints

Primary

Effectiveness:

For both MCC, MCC-T and EGD, rates of diagnosis of clinically relevant pathology in patients with upper abdominal pain will be assessed. Detection of D2 findings will be considered positive. Sensitivity, specificity, positive predictive value, and negative predictive values will be calculated for both MCC and EGD. In this study the “gold standard” will be the expert group’s decision regarding the presence of an abnormal finding. McNemar’s test will be used to assess for statistically significant differences between the two modalities. Sub-analyses will be performed to compare accuracies of the two modalities based on anatomic region (i.e. esophagus, stomach, duodenum) and across various lesions (i.e. ulcers, gastropathy, esophagitis, etc.).

Safety: Rate of device or procedure related adverse events during the procedures or in the follow-up period (24 hrs. post procedure).

Secondary

Examination completion: Compare rates of complete examination of the foregut by MCC or MCC-T and EGD in patients presenting with upper abdominal complaints using sets of predetermined still images

Patient Satisfaction: Assess patient satisfaction for patients undergoing MCC or MCC-T and EGD.

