12.3 Criteria for Removal from the Study

The investigator may withdraw subjects from the study as is deemed necessary or deemed to be in the best interests of the subject, such as,

- continued noncompliance with the protocol or study visits,
- severe illness or disability during the study for non-study issues,
- pursuit of subsequent alternative treatment for the same condition, or
- development of intolerable side effects where continued follow-up becomes too burdensome.

In addition, a subject may also choose to exit the study at any time but will be strongly encouraged to participate in the follow-up telephone call for safety reasons.

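### No safety contact outside a procedure visit is timed from the capsule: with a delayed EGD its 24-hour window is first queried up to 6 days late, and a subject who never has EGD has no stated trigger for any contact

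*Combined protocol and SAP*

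**What the plan says.** The primary safety endpoint in 4.2 (and in the synopsis) is "Rate of device or procedure related adverse events during the procedures or in the follow-up period (24 hrs. post procedure").

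The order and spacing of the two procedures are in 6.4: "The MCC or MCC-T will be performed first followed by an EGD at least 2-3 hours later, but up to 7 days later". Section 6.5 allows both on one day where practicable and otherwise EGD within 7 days.

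The schedule in 6.2 marks an adverse-event evaluation at Visit 2 (capsule), Visit 3 (EGD) and Visit 4 (telephone). Section 6.6 times Visit 4: "24 hours after all procedures are completed the study coordinator will call the patient". Section 5.3 gives a wider interval, "including follow-up 24-72 hrs. after the final study related procedure". Both count from the last procedure.

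For early leavers, 12.3 says that "a subject may also choose to exit the study at any time but will be strongly encouraged to participate in the follow-up telephone call". Among the reasons for removal by the investigator it lists "development of intolerable side effects where continued follow-up becomes too burdensome", and it does not say whether the call is then made.

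Section 10.2 restricts the safety population to subjects who had both the tethered capsule and EGD.

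**The concern.** Primary objective 2 compares capsule safety with EGD safety. A fair comparison needs the two procedures' events to be sought with similar promptness. The call is anchored to whichever procedure comes last, and that is always EGD. The capsule has no follow-up contact of its own; post-capsule events wait for the EGD visit.

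This matters because the capsule events expected here are mostly minor and short. Section 2 says of the larger previous study: "All reported symptoms were resolved within 24 hours after ingestion of the capsule". A patient seen several days later would probably be well again, so detection would depend on recall.

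A subject who swallows the capsule and does not go on to EGD is a separate gap. No Visit 3 takes place, and the condition for the call is never met. If a capsule problem is the reason EGD did not happen, the missing contact is related to the outcome being measured.

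**Working it through.** The plan gives no figure to reproduce on this point. The check is timeline arithmetic.

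**Inputs.** Capsule-to-EGD gap g: 2 to 3 hours minimum, 168 hours (7 days) maximum (6.4). Delay d from the last procedure to the call: 24 hours (6.6), or 24 to 72 hours (5.3). Endpoint window: 24 hours (4.2).

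**Formulas.** Lag of the Visit 3 check past the capsule window = g − 24 h. Lag of the call past the capsule window = g + d − 24 h. Lag of the call past the EGD window = d − 24 h.

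| Gap g | Visit 3 check | Call with d = 24 h | Call with d = 72 h |
|---|---|---|---|
| 2 h | before window closes | 26 h after capsule; 2 h past window | 74 h; 2.1 days past |
| 3 h | before window closes | 27 h; 3 h past | 75 h; 2.1 days past |
| 24 h | as window closes | 48 h; 1 day past | 96 h; 3 days past |
| 72 h | 2 days past | 96 h; 3 days past | 144 h; 5 days past |
| 168 h | 6 days past | 192 h; 7 days past | 240 h; 9 days past |

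For EGD the call is 24 − 24 = 0 days past the window under 6.6, or at most 72 − 24 = 48 h (2 days) under 5.3. At the longest gap, then, the first enquiry after the procedure visit is 6 days late for the capsule and 0 to 2 days late for EGD. With same-day procedures and the 6.6 timing there is no material difference.

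**Subject without EGD.** Visit 3 does not occur, and d is counted from an event that never happens. Neither later contact has a defined time. The only relevant text is the encouragement in 12.3, which is written for those who choose to leave.

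**Sensitivity of the rate to one event (illustration, not a forecast).** Section 2 reports adverse events in 5 of 350 patients: 5/350 = 1.43%, matching the stated 1.4%. If that rate applied to the 70 patients in 10.6, the expected number affected is 70 × 0.0143 = 1.0, and the probability of at least one is 1 − (1 − 0.0143)^70 = 0.63. With one event the estimate is 1/70 (95% Clopper-Pearson interval 0.04% to 7.7%). If that patient had no EGD and dropped out under 10.2, it becomes 0/69 (0% to 5.2%). At counts this small, one unrecorded event separates some capsule events from none.

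**The case against.** The strongest reply is that most patients are covered. Section 6.2 schedules an adverse-event evaluation at Visit 3, after the capsule, and items 7 and 8 of the Appendix I questionnaire ask about capsule problems during and after the test. Section 6.5 allows same-day procedures where practicable, and the footnote to 6.2 treats a longer gap as a contingency. This stands: a reader might infer from 6.6 that the call is the only safety contact after the capsule, and 6.2 shows that it is not. It does not remove the delay for split-day patients.

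A reader might also infer from 12.3 that subjects removed by the investigator are denied the call. The section is silent rather than exclusionary. An investigator who removes someone for side effects already knows of the event, and 9.2 requires it to be investigated and documented. What remains is that no later contact is stated for such a subject. The general promise in 9.2 of careful monitoring names no contact and no time.

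It is tempting to project how many affected patients would be missed. The documents do not support that. In the earlier studies in section 2, (1 + 3)/(100 + 353) = 4/453 = 0.9% of subjects refused endoscopy. That shows it can happen, but those endoscopies were unsedated, whereas 6.5 provides sedation here. Even taking that rate and assuming independence, 70 × 0.0088 × 0.0143 is about 0.01 affected patients without EGD. Nor do the documents give evidence on how far recall fades over six days.

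Finally, the flow diagram in 6.1 and the appended timeline are not visible here, and the consent pages were removed. The claim is therefore limited to the text available.

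**Conclusion.** The concern holds in a limited form. No contact outside a procedure visit is timed from the capsule. For split-day patients the first enquiry about post-capsule events can be up to 6 days after the endpoint window closes, and the call up to 7 days after it under 6.6 or 9 days under 5.3. A subject who never has EGD has no stated trigger for any post-capsule contact.

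If delayed enquiry loses events, as is plausible for brief symptoms, the loss favours the capsule in a primary safety comparison. The size of the effect is unknown because it depends on the share of split-day patients and of subjects without EGD, and the documents give neither. The safety analysis is descriptive (10.4) and the trial is a pilot, so no test or decision threshold is affected. This is a worthwhile, inexpensive improvement in data collection rather than a defect that undermines the study.

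**What to change.** - **6.2 and 6.6:** add a safety call 24 hours after the capsule for every subject whose EGD has not taken place by then, and keep the existing call after EGD.
- **6.6 and 12.3:** state that a subject who swallowed a capsule and does not reach EGD, including one removed by the investigator, still receives the safety call and completes the Exit Form. The criteria for removal need not change.
- **10.2:** analyse capsule safety in everyone who swallowed a capsule, with or without a tether, whether or not EGD followed. Without this, an event collected by the new call would still be left out of the analysis. Equally, changing 10.2 alone would add subjects whom nobody had asked.
- **Synopsis, 4.2, 5.3 and 6.6:** reconcile the 24-hour and 24-to-72-hour statements of the follow-up time.

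The cost is one short call by the existing coordinator for some patients, plus protocol wording. The capsule event rate may come out slightly higher.
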